To develop, evaluate, and test a risk score for the presence of opioid misuse behavior from documentation in the electronic health record including structured data such as encounters, diagnoses and prescriptions, and incorporating unstructured, free-text clinical documentation. The resulting risk score will be used as an outcome measure in the pilot study.

Study Design & Methods

Aim 1

We will conduct several study sessions involving 2 Standardized Patients (SPs), each portraying different cases, who will be seen by 2 primary care providers (PCPs) per session. SPs are healthy individuals trained to consistently and reproducibly portray patients in medical or communication-based scenarios. Each encounter will simulate a patient-PCP appointment in which the PCP must address opioid misuse behaviors exhibited by the SP. To ensure consistency across sessions and facilitate productive group interviews, each session will feature the same 2 SPs. The sessions will last five hours, including a half-hour orientation, three consecutive hour-long SP encounters, an hour-long group interview, and short breaks. These sessions will be conducted virtually via Zoom.

At the beginning of each session, PCP participants will be consented, enrolled in the study, and will complete a demographic and practice characteristics survey, along with questions about their knowledge and attitudes toward treating chronic pain and addiction. The surveys will be adapted from previous work and conducted via REDCap. During the study, PCPs will use the algorithms provided to create treatment plans for managing the concerning behaviors exhibited by the SPs. Each case will focus on one branch of an algorithm, but PCPs will have access to laminated cards (sent via email) containing all algorithms to simulate real-world decision-making.

Study staff will facilitate the Zoom sessions, utilizing breakout rooms for the SP encounters. PCPs will have 15 minutes to review patient information, such as urine drug tests and prescription monitoring data, and evaluate the patient. They will see patients longitudinally up to 3 times, with 5-minute intervals between each visit to write orders for lab tests, referrals, and medications, and complete a brief electronic survey. The longitudinal case will take

approximately 60 minutes in total. After each SP encounter, PCPs will participate in a structured group interview to discuss the session.

Aim 2

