We will conduct a pilot trial at 3 UPMC sites: 2 UPMC CMI community primary care practices and 1 UPMC Presbyterian practice, to assess the feasibility, acceptability, and preliminary effectiveness of the algorithms. All PCPs at each site will participate. The pilot trial aims to mimic key elements of the future effectiveness-implementation hybrid trial, including PCP recruitment and consent, PCP orientation to the algorithms, and outcome assessment. The intervention will be implemented at the pilot sites for 6 months or longer, depending on the clinic's discretion.

A survey will be administered to PCPs to assess algorithm use, asking which algorithms were used, how often, and any resulting changes in outcomes, such as opioid dose reduction. The primary feasibility benchmark will be that 80% of PCPs report using at least one algorithm during the study period. Feasibility and acceptability will also be assessed qualitatively through interviews with the PCPs.

In addition to the study sessions, algorithm integration into the Electronic Health Record (EHR) will be developed through the Electronic Health Record Research Request (R3). For the development of an opioid misuse risk score, we will conduct a retrospective analysis of EHR data, including structured and primary care textual documentation, for patients engaged in primary care at the practices enrolled in the overall study. This analysis will include clinical records of all patients prescribed chronic opioid therapy. We will extract both structured and textual data from the EHR and identify patients who developed opioid use disorder (OUD) using encounter diagnoses. Additionally, patients with documented evidence of opioid misuse behavior will be identified through clinician chart review.

To develop the risk score, we will apply machine learning techniques to identify over-represented terms, phrases, and concepts in the textual documentation of patients who developed OUD or exhibited opioid misuse behaviors. The structured and scored textual data will then be fed into further machine learning algorithms to create a risk score specifically tailored for the practices participating in the study. This risk score for opioid misuse and OUD will then be used as an outcome measure in the pilot study of the consensus-based algorithm to address opioid misuse behaviors.

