To improve the model, we may use a sample of notes from patients identified with opioid misuse behaviors, which will be de-identified by an honest broker before integration into the training data set for the machine learning model.

After completing Aim 1, we will pilot an implementation strategy bundle for the algorithms in three clinics. The pilots will be staggered, so they do not all begin simultaneously. Each pilot will last six months, and the clinics will maintain access to some materials, such as the website, even after the pilot period is complete.

Inclusion Criteria

Aim 1:

Primary care providers at UPMC practices
18 years+

Aim 2:

-Providers from the 4 identified pilot sites for Aim 2
-Patients from the 4 identified pilot sites who are on long-term opioid therapy (LTOT)
-18 years+

Exclusion Criteria

Aim 1:

Non-UPMC affiliates, trainees (residents and fellows), those with < 2 years of experience, and PCPs from the practices identified as pilot sites in Aim 2

Aim 1 and Aim 2:

Children under 18 years of age

Statistical Analysis Plan

Aim 1: As 2 SP cases will be presented per session, 12 SP sessions will be required to present all 23 cases. Group interviews will be analyzed using thematic analysis. There may be cases that we would like to revisit, either because we did not receive sufficient feedback or because feedback from subsequent cases makes it useful to revisit an earlier case.

Aim 2: For EPIC tool usage report, analysis will be conducted in the following way:

- Monitoring the number of total encounters within the past 2 weeks
- For sub-group analysis: exclude people with 32 or fewer encounters per week
- For these encounters, obtain data on use of Epic tools designed for the study, which are documentation tools and decision and ordering support
- Analyses will be conducted by provider but de-identified

Analysis for Aim 2 will be conducted using descriptive statistics and pre/post analysis. The effectiveness of the implementation strategy bundle will be analyzed using t-tests to compare outcomes at pre- and post-intervention with baseline values.

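### Aim 2 effectiveness rests on t-tests with no stated unit, pairing, clustering allowance or outcome window, although the EHR risk score appears to be measured on patients nested in PCPs and clinics

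*Combined protocol and SAP*

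**What the plan says.** The Statistical Analysis Plan for Aim 2 opens with a list for the Epic tool usage report, which includes "Analyses will be conducted by provider but de-identified". It then says "Analysis for Aim 2 will be conducted using descriptive statistics and pre/post analysis", and that effectiveness will be "analyzed using t-tests to compare outcomes at pre- and post-intervention with baseline values". That last sentence does not list its outcomes.

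On the risk score, Study Objectives (Integrate algorithms into the EHR) says "The resulting risk score will be used as an outcome measure in the pilot study", and Study Design & Methods, Aim 2, repeats the point. On how the score is developed, the latter section says "This analysis will include clinical records of all patients prescribed chronic opioid therapy". The Inclusion Criteria list LTOT patients among the Aim 2 subjects, and every PCP at each site takes part.

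On timing, Study Design & Methods says "The intervention will be implemented at the pilot sites for 6 months or longer", at the clinic's discretion. A later paragraph of the same section gives each pilot a length of six months and adds: "The pilots will be staggered, so they do not all begin simultaneously". The design text counts three sites; the Inclusion Criteria count four.

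**The concern.** The intervention works through PCPs, so patients of the same PCP can be expected to change together. A t-test that treats their scores as independent would then give an interval that is too narrow. A two-sample t-test on the same patients before and after would ignore the correlation between each patient's two scores, which pushes the error the other way. The plan does not say which test is meant, so the choice could be made after the data are seen.

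The contrast is also loosely worded, because pre-intervention and baseline appear as if they were different time points. The mention of a pre/post analysis makes post versus pre the likely reading, but no look-back or post-assessment period is given.

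Preliminary effectiveness is one of the pilot's three stated purposes, and the pilot is meant to rehearse the outcome assessment of the later hybrid trial.

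**Working it through.** The plan states no Aim 2 sample size, alpha, ICC or correlation, so it has no figure to reproduce. All inputs below are assumed: two-sided nominal 5%, m patients per PCP, ICC of the within-patient change among patients of one PCP, and pre/post correlation r.

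**Paired t-test on patients.** The true variance of the mean change exceeds the assumed variance by DE = 1 + (m − 1) × ICC. The actual type I error is 2 × P(Z > 1.96/√DE).
- m = 20, ICC 0.02: DE = 1 + 19 × 0.02 = 1.38; 1.96/√1.38 = 1.668; error 9.5%.
- m = 20, ICC 0.05: DE = 1 + 19 × 0.05 = 1.95; 1.96/√1.95 = 1.404; error 16.0%.

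Simulation (10,000 runs per setting, 3 clinics, 10 or 20 PCPs) gave 9.3% to 16.6% with equal panels, and 10.1% to 18.5% with panels of 5 to 35 patients.

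**Unpaired t-test on the same patients.** The ratio of true to assumed variance is (1 − r) × DE.
- No clustering, r = 0.5: ratio 0.5; 1.96/√0.5 = 2.772; error 0.56%.
- No clustering, r = 0.7: ratio 0.3; 1.96/√0.3 = 3.578; error 0.03%.
- m = 20, ICC 0.02, r = 0.7: 0.3 × 1.38 = 0.414; error 0.23%.
- m = 20, ICC 0.05, r = 0.5: 0.5 × 1.95 = 0.975; error 4.7%.

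This test becomes liberal only when (1 − r) × DE exceeds 1. For example, m = 30, ICC 0.10 and r = 0.5 give DE = 3.9 and a ratio of 1.95, hence 16.0%.

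**t-test on PCP mean changes.** In the same simulation, with no clinic-level shifts, the error was 4.7% to 5.5%.

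**Clinic-level shifts.** Let each clinic have its own shift, with variance 1% to 2% of the change variance (3 clinics of near-equal size). Two targets must be kept apart:

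| Analysis of PCP mean changes | Misses the average of the participating clinics | Rejects zero change beyond these clinics |
|---|---|---|
| Plain one-sample t-test | about 3.4% to 4.5% | about 8% to 20% |
| Clinic as sum-to-zero fixed effect | about 5% | about 8% to 24% |

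Both versions are sound for the participating clinics, and neither is sound beyond them.

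**Width of the interval against the paired patient-level interval**, 20 patients per PCP, K PCPs, DE 1.38 to 1.95.
- Plain PCP means: √DE × t(.975, K − 1)/t(.975, 20K − 1). K = 20: 2.093/1.966 × (1.175 to 1.396) = 1.25 to 1.49. K = 10: 2.262/1.972 × (1.175 to 1.396) = 1.35 to 1.60.
- Clinic-adjusted: use t(.975, K − 3) and multiply by √(K × Σ(1/Kj)/9), where Kj is the number of PCPs in clinic j. K = 20 (7, 7, 6): 1.26 to 1.50. K = 10 (4, 3, 3): 1.42 to 1.69.

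**The case against.** The strongest reply is that no patient-level t-test is actually written. The sentence concerns the implementation bundle and unnamed outcomes, and the only unit in the Statistical Analysis Plan is the provider. If that unit was meant throughout, the PCP-level problem does not arise. This stands as a limit on the point. It does not remove it, because the provider statement sits in the Epic usage list and nothing says how patient scores would be summarised per provider.

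A second reply is that six months supplies the window. It is the length of the pilot, not an outcome window. Equally, a reader might infer from the open-ended wording that exposure must vary by clinic. The later six-month statement does not support that, and the two passages need reconciling.

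A third reply is that this is a small pilot and a t-test is adequate. Much of that stands: run on PCP mean changes, the plan's own method is adequate for the participating clinics. A reader might think that clinic adjustment is needed to protect against clinic-level shifts. The comparison above shows otherwise with near-equal clinics: the plain test covers the participating-clinic average, and for the wider target the adjusted test rejects slightly more often.

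**Conclusion.** The gap is real and worth fixing, with medium confidence. The sentence leaves unit, pairing, clustering and windows open for an outcome that is very probably patient-level. Under the assumed inputs, a paired patient-level test has a type I error of 9.5% to 16.0%. An unpaired test on the same patients, with positive pre/post correlation and no clustering, has 0.03% to 0.6%.

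Three stronger readings are not supported.
- That the trial's result is biased: the documents give no PCP counts, patient counts or correlations, and the risk score's level and its use in the t-test are inferred. The figures show only that the choice can matter.
- That an unpaired test can err in either direction even without clustering: with positive pre/post correlation it is then conservative only.
- That the feasibility conclusion is at risk: the 80% PCP benchmark does not use the t-test.

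The simulations assume three clinics. The conflict between three and four sites must be reconciled, since it sets the number of top-level clusters. Neither number allows strong inference about clinics in general.

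**What to change.** Replace the sentence with one contrast, post-intervention versus pre-intervention, using windows of equal fixed length anchored to each clinic's own start date. Name the outcomes it covers. Reconcile the two statements of pilot length and the two site counts.

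For the risk score:
- assign each patient to one PCP at baseline;
- compute each patient's change, average it per PCP, and apply a one-sample (paired) t-test to the PCP mean changes. A mixed model on within-patient change with a PCP random intercept does the same job, with a t reference based on the number of PCPs;
- treat clinic as a sum-to-zero fixed effect only if wanted. It is useful when clinics differ much in number of PCPs, because it targets the unweighted clinic average.

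For PCP-level outcomes, test pre/post pairs only where a pre-intervention value is collected. The survey is described as "asking which algorithms were used, how often, and any resulting changes in outcomes, such as opioid dose reduction", with no pre-intervention round, so otherwise report those outcomes descriptively. Give estimates with confidence intervals, label them preliminary and limit them to the participating clinics.

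The cost is SAP wording, fixed windows and a patient-to-PCP attribution rule, applied to EHR data already planned for extraction. The downside is a wider interval: about 1.3 to 1.7 times the patient-level paired interval for the clinic-adjusted version with an assumed 10 to 20 PCPs, and somewhat less for the plain test on PCP means.
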